8.0 Patient Randomization

Patients will be randomized to the MIRI-TL group (MIRI) or the Standard culture group (SC) by randomization number generator through www.randomizer.org, using a number set from 1 to 500. Numbers 1-300 will be assigned to the study (MIRI-TL) group while numbers 301-500 will be assigned to the control (Standard Incubator).

8.1 Egg Retrieval and Fertilization-Day 0

Egg retrieval and fertilization follow the standard protocol in place at the clinical site. Insemination, by intracytoplasmic sperm injection (ICSI) will take place on Day 0 (egg retrieval day) following standard protocol currently in place at the clinical site. The fertilized eggs should be free of cumulus cells as much as possible. If the cumulus cells remain in place, they may interfere with the quality of the imaging. Immediately after micro insemination, eggs will be placed in individual wells within a CultureCoin (MIRI group), or a standard culture dish (SC group), and incubated in the MIRI-TL or standard incubator respectively. All eggs will be cultured in the standard fertilization media currently in place at the clinical site. At 20hr after insemination, the MIRI-TL imaging software will be Paused, and all embryos will be examined by the embryologist for successful fertilization (2PN). All normally fertilized eggs will be placed into a new CultureCoin (MIRI group) or standard culture dish (SC group) containing the standard embryo culture media, and incubated in the MIRI-TL or standard incubator respectively.

Once an embryo is assigned a micro-well location, it must remain in the same location throughout the study imaging period. Embryos assigned to the MIRI group will be imaged in the CultureCoin from Day 0 to Day 7. Images of the developing embryos will automatically be captured with the MIRI-TL Microscope. Data collected will include the following:

- Number of eggs inseminated

- Fertilization method
- Total number of fertilized eggs (2PN)

8.2 Day 3 Embryo Assessment

At Day 3, the MIRI-TL imaging software will be Paused and the embryologist will evaluate embryos from both groups per standard procedure. The development stage of the embryos and grading based on traditional morphology criteria will be recorded. It is recommended that the Day 3 morphology assessment is done within 48 hours after the fertilization (2PN) check. ***Per protocol, Assisted Hatching (AH) is allowed if patients have opted for embryo biopsy and PGS.***

After embryo assessment the embryos may be placed back into the MIRI-TL or standard incubator as per their respective groups, and imaging will be resumed for the MIRI group.

8.3 Day 5, 6 and 7 Embryo Assessment

The embryologist will evaluate the embryos using traditional morphological grading. It is recommended that the Day 5 morphology assessment is done within 48 hours after the Day 3 morphology assessment.

8.4 Embryo Biopsy and Preimplantation Genetic Screening Data - if applicable

Pre-implantation Genetic Screening (PGS) is not required in this study. If the physician and the patient have previously decided to perform PGS in the IVF cycle, the outcome data will be collected. Embryo biopsy and PGS will be performed per standard procedure. Transfer procedures and disposition of embryos not selected for transfer will be determined as per the standard protocol in place at the time of the study.

8.5 Embryo Transfer

Embryo(s) will be selected for transfer based on the current standard protocol in place at the clinical site. Data pertaining to the embryo transfer procedure will include the following:

- Day and date of transfer
- Total number of embryos transferred
- Luteal phase support

8.6 Outcome: Pregnancy Test

After embryo transfer, each subject will be followed to determine if a chemical pregnancy has been achieved by undergoing the clinical sites' standard serum pregnancy testing procedure. Data will be recorded and include the following:

- Date of the serum pregnancy test
- Quantitative hCG level

Each subject with a positive serum pregnancy test result will continue to be followed. If the result of the pregnancy test is negative, the subject will have completed the study and be exited at that time.

8.7 Outcome: Pregnancy Confirmation Ultrasound

A clinical pregnancy is typically verified by the detection of a fetal heartbeat via vaginal ultrasound. The clinical site verifies clinical pregnancy at approximately 5-8 weeks gestation. The results of the test will be recorded and include the following:

- Date of ultrasound
- Result of initial pregnancy ultrasound
 - Number of intrauterine gestational sacs
 - Number of fetal heart beats

If the result of the ultrasound is negative, that is, if no fetal heartbeat is detected, then the subject will have completed the study and be exited at that time.

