Indications for Use/Intended Use	The MIRI-TL is a purpose built embryo culture incubator using a built-in microscope and camera designed specifically for the continuous assessment of embryo development in-vitro . As images are digitally obtained and stored, a video can be generated to enable more objective and reliable grading criteria. This technology, in conjunction with the MIRI-TL Viewer allows for non-invasive viability evaluation and assessment allowing for better prediction of embryo developmental potential and implantation success. The MIRI-TL is CE marked for clinical use. The CultureCoin is intended to be used to hold human oocytes and embryos during handling and culture.
Study Purpose	The purpose of this study is to demonstrate and validate the non-inferior or superior safety and efficacy of the MIRI-TL compared to standard big-box incubators used for embryo culture.
Study Design	Prospective, observational, randomized, double-arm

Safety Measures	Adverse events and device malfunctions will be reported and summarized from the start of embryo culture through study exit.
------------------------	---

Number of Subjects	Up to 500 patients
Subject Population	Patients undergoing in vitro fertilization treatment who fulfill all eligibility criteria.
Eligibility Criteria	
Inclusion Criteria:
 
 • At least 18 years of age • Women undergoing in vitro fertilization treatment using their own or frozen oocytes • Fresh or Frozen Embryo Transfer • Fertilization by ICSI • At least 4 diploid (2PN) embryos at fertilization check • Willing to have all inseminated oocytes imaged by Miri • Willing to comply with study protocol and procedures • Willing to provide written informed consent 
Exclusion Criteria:
 
 • Fertilization using surgically removed sperm • History of cancer
Number of Sites	1
Study Duration	Expected study duration is 18 months including enrollment and follow-up. Subjects will be followed until pregnancy outcome has been determined (i.e. date of negative hCG test, 8-12 week clinical pregnancy ultrasound, or date of live birth, if pregnant).
Summary of Data Collection	
 • Enrollment: Demographics, IVF and pregnancy history • IVF Lab: Embryo morphology • Time-Lapse Imaging Data • Pregnancy test and Live Birth Outcome • Preimplantation Genetic Screening (PGS) Data, if applicable • Frozen Embryo Transfer (FET) Data, if applicable

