4.1 CultureCoin

The 16-well CultureCoin (**Figure 2**) is a standard size (60mm) embryo culture dish with individual micro-wells aligned in a row in the center of the dish. Each micro-well is designed to accommodate a single patient's oocytes or developing embryos through the blastocyst stage and are culture individually. The 16-well CultureCoin is designed to fit in only one (1) position in one (1) of the individual six (6) incubator chambers, and each micro-well is identified to facilitate embryo tracking (for example, micro-well

Figure 2: CultureCoin

5. Number of Centers and Study Duration

The TiMMI study will include only one investigational site. This site will conduct the study under a single clinical investigation plan.

Expected study duration is 18 months including enrollment and follow-up. Subjects will be followed until pregnancy outcome has been determined (i.e. date of negative hCG test or 8-12 week clinical pregnancy ultrasound, if pregnant).

6. Study Design

This is a prospective, non-blinded, observational, randomized, double-arm study.

7. Statistical Methods and Analyses

Up to 500 subjects' embryos will be collected in this ongoing data collection protocol. We aim to recruit 200 patients in the standard culture group, and 300 patients in the MIRI-TL group.

Assuming that 25% of all inseminated oocytes would develop into blastocysts (based on published clinical data), at least 1300 inseminated oocytes (~163 patients) would be needed in each group to detect an increase in blastocyst proportion of 20% with 80% power and a significance level of 0.05 (two-tailed tests).

Assuming that time from insemination to start of blastulation (tSB) follows a normal distribution, and is 96h with a variance of 49h in euploid embryos, and 98h (variance 49h) in aneuploid embryos, ~405 blastocysts (1620 inseminated oocytes = 203 patients) in the MIRI-TL group will need to be biopsied to detect a significant difference in tSB (80% power, 0.95 confidence level, 2-tailed test). Since ~80% of all patients receive PGS at our clinical site, we will need ~255 patients in our MIRI-TL group.

To account for patient dropout and lower than expected oocyte retrieval per patient, we propose to recruit up to 500 subjects in this ongoing data collection protocol: 200 patients in the standard culture (SC) group and 300 patients in the MIRI-TL (MIRI) group.

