8.8 Outcome: Ongoing Pregnancy Ultrasound

The clinical site verifies the viability of the pregnancy (ongoing pregnancy) at approximately 8-12 weeks gestational age via vaginal ultrasound. Data will be recorded and include the following:

- Date of ultrasound
- Result of ultrasound
 - Number of gestational sacs
 - Number of fetal heartbeats
- Pregnancy outcome

If the result of the ultrasound is negative, that is, if an ongoing pregnancy is not confirmed, then the subject will have completed the study and be exited at that time.

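### Section 8.7 ends study follow-up when no heartbeat is seen at about 5–8 weeks, an exit that the synopsis and Section 5 do not contain

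*Combined protocol and SAP*

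**What the plan says.** Section 8.7 of the combined protocol and SAP gives the timing of the first scan: "The clinical site verifies clinical pregnancy at approximately 5-8 weeks gestation". Its criterion is that "A clinical pregnancy is typically verified by the detection of a fetal heartbeat via vaginal ultrasound". The data recorded are the scan date, "Number of intrauterine gestational sacs" and, as a separate count, heartbeats. A scan without a heartbeat is called negative, and the section then says: "if no fetal heartbeat is detected, then the subject will have completed the study and be exited at that time".

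The other passages on follow-up are these:

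- Section 8.6 keeps every woman with a positive serum test in follow-up.
- Section 8.8 says: "The clinical site verifies the viability of the pregnancy (ongoing pregnancy) at approximately 8-12 weeks gestational age via vaginal ultrasound".
- The synopsis (Study Duration) follows women until the pregnancy outcome is known, and spells this out as "date of negative hCG test, 8-12 week clinical pregnancy ultrasound, or date of live birth, if pregnant".
- Section 5 spells it out as "date of negative hCG test or 8-12 week clinical pregnancy ultrasound, if pregnant", without live birth.
- Section 3.2 makes pregnancy test and live birth data a secondary objective. Section 3.1 makes safety and imaging data the primary one.
- Section 8.12 reports adverse events up to each subject's completion of the study, and follows a reported event until it resolves or stabilises.

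**The concern.** The exit in 8.7 depends only on the heartbeat. A woman with one or more intrauterine sacs and no heartbeat is treated in the same way as a woman with an empty scan, wherever in the 5–8 week window the scan falls. If some pregnancies scanned early in that window do not yet show a heartbeat and later continue, they leave the study before the scan at which the plan itself checks viability.

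Three kinds of data are then at stake for these women: the 8–12 week result, the live birth record, and any adverse event that begins after exit. Whether a pregnancy is followed to its outcome would depend partly on the date for which the first scan was booked. If such women are also counted as not pregnant, both arms' ongoing pregnancy rates fall and the difference between them shrinks. That costs power for superiority and makes non-inferiority easier to conclude, and the synopsis names both aims.

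**Working it through.** **1. The passages side by side.** After a positive hCG test, the plan gives these points at which follow-up ends:

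| Place | Ends of follow-up after a positive hCG |
|---|---|
| Synopsis, Study Duration | 8–12 week scan, or live birth |
| Section 5 | 8–12 week scan |
| Section 8.7 | scan at about 5–8 weeks, if no heartbeat |
| Section 8.8 | scan at about 8–12 weeks, if ongoing pregnancy is not confirmed |

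The 8.7 exit has no counterpart in the synopsis or Section 5. Those two also attach the term clinical pregnancy ultrasound to 8–12 weeks, whereas 8.7 attaches clinical pregnancy to 5–8 weeks. Section 8.7 gives no repeat scan and no category for a sac without a heartbeat, although its data fields would identify one.

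**2. What exit removes.** Under 8.7 the woman has completed the study, so 8.8 no longer applies to her and no live birth record follows. Under 8.12, reporting of new adverse events stops at completion. An event already reported is still followed.

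**3. Is there a planned figure to reproduce?** No. The two sample-size calculations in Section 7 concern the blastocyst proportion and the time to start of blastulation in euploid and aneuploid embryos. Pregnancy enters neither, and no planned figure changes.

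**4. Possible size, on assumptions.** Let p be the true ongoing pregnancy rate per randomised woman. Let m be the share of those pregnancies that show no heartbeat at the first scan, are exited, and are counted as not ongoing. The documents give neither. Then:

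- observed rate = p × (1 − m)
- pregnancies exited = n × p × m
- observed difference = true difference × (1 − m), if m is the same in both arms

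Inputs from Section 7 are n = 200 (standard culture) and n = 300 (MIRI-TL); Section 8 of the same text is not needed, and the two-sided level of 0.05 is the plan's. Assumed inputs are p = 40% (standard culture) and 50% (MIRI-TL), and m from 0 to 20%. Power uses the normal approximation for two proportions, with pooled variance under the null.

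| m | Standard culture | MIRI-TL | Difference (points) | Exited, of 200 / of 300 | Power |
|---|---|---|---|---|---|
| 0 | 40.0% | 50.0% | 10.0 | 0 / 0 | 59.5% |
| 2% | 39.2% | 49.0% | 9.8 | 1.6 / 3.0 | 57.9% |
| 5% | 38.0% | 47.5% | 9.5 | 4.0 / 7.5 | 55.5% |
| 10% | 36.0% | 45.0% | 9.0 | 8.0 / 15.0 | 51.7% |
| 20% | 32.0% | 40.0% | 8.0 | 16.0 / 30.0 | 44.2% |

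For example, at m = 10% the standard culture rate is 0.40 × 0.90 = 36.0%, and 200 × 0.40 × 0.10 = 8 pregnancies are exited. At m = 0 nothing is lost.

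**The case against.** The best defence is that the passages can be read together. The synopsis and Section 5 follow a woman until her outcome is known and apply the 8–12 week scan only if she is pregnant; 8.7 could be read as saying that a scan without a heartbeat settles the matter. The words typically and initial in 8.7 also leave some room for a later scan. This shows that the conflict may be a drafting gap and not a deliberate choice. It does not remove it. The exit sentence is unconditional, and 8.8 assigns viability to 8–12 weeks, so a sac without a heartbeat early in the window is not clearly a settled outcome.

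Other parts of the defence stand:

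- A reader might infer that viable pregnancies are in fact recorded as failures. The documents do not say so. They do not state when a heartbeat becomes visible, when in the window scans are done, or how exited women are counted. Sacs, heartbeats and dates are recorded, so the affected women could be found in the data.
- A reader might take the 8–12 week scan as the trial's pregnancy endpoint. It is given only as one of the ends of follow-up, and no pregnancy endpoint is defined.
- A reader might infer that the morphokinetic analysis is corrupted. Section 3 speaks of relating morphokinetics to success rates, but the one analysis of this kind specified in Section 7 compares euploid with aneuploid embryos and uses no pregnancy result.
- A reader might infer that ectopic pregnancies and losses escape safety reporting because of this exit. Section 8.12 leaves out events well documented for IVF in the clinic's consent, so these may not be collectable in any case.
- Nothing suggests that scan timing differs between the arms.

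**Conclusion.** The point holds as a conflict between passages with a possible loss of outcome data. Section 8.7 contains an exit that the synopsis and Section 5 lack, and it can end follow-up before the pregnancy outcome is known. If it is followed as written, such women lack the 8–12 week and live birth results, and their new adverse events are not collected.

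The size is unknown. It rests on the share of continuing pregnancies without a visible heartbeat at the first scan, which the documents do not give. It could be near zero if scans are booked late in the window. Over the assumed range of 2% to 10%, power in the example falls from 59.5% to between 57.9% and 51.7%; only the assumed extreme of 20% costs much more. These figures further assume that exited women are counted as not ongoing and that both arms are affected equally.

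The outcomes affected are secondary, apart from new adverse events, which belong to the primary objective. Neither sample-size calculation is touched. The conflict should be corrected because the text is clear and the correction is cheap, not because a large bias has been shown.

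**What to change.** Reconcile 8.7 with the synopsis and Sections 5, 8.6 and 8.8, as follows:

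- The 5–8 week scan records sacs, heartbeats and date. It does not by itself end study follow-up while the outcome is undetermined, and the text states how a sac without a heartbeat is classified in the data.
- Study follow-up, including collection of new adverse events, continues until a documented pregnancy outcome: a documented loss or other end of pregnancy, the 8–12 week result, and live birth as the synopsis and Section 3.2 require. Section 5 needs the live birth entry added so that it agrees with the synopsis.
- The between-arm comparison of ongoing pregnancy uses the 8–12 week result, with all randomised subjects as the denominator.

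This concerns study data only; when scans are done and how patients are managed stay with the site. The cost is a few sentences. Section 8.8 already describes the 8–12 week scan as site practice and already has the data fields. The small downside is somewhat longer data follow-up for a few women.

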8.8 Outcome: Ongoing Pregnancy Ultrasound

The clinical site verifies the viability of the pregnancy (ongoing pregnancy) at approximately 8-12 weeks gestational age via vaginal ultrasound. Data will be recorded and include the following:

- Date of ultrasound
- Result of ultrasound
 - Number of gestational sacs
 - Number of fetal heartbeats
- Pregnancy outcome

If the result of the ultrasound is negative, that is, if an ongoing pregnancy is not confirmed, then the subject will have completed the study and be exited at that time.

8.9 Frozen Embryo Transfer (FET) Cycles – if applicable

If the patient does not get pregnant from the fresh embryo transfer, data from blastocysts previously frozen in the fresh cycle may be thawed for a FET for the duration of the study. Endometrial preparation for FET cycles will be performed per the clinical sites standard protocol. Data pertaining to the stimulation protocol, pregnancy, and outcome data will be collected.

8.10 Protocol Deviations

A protocol deviation occurs when a clinical investigator and/or study site personnel does not conduct the study according to the clinical investigation plan. All deviations are recorded on the **Protocol Deviation** case report form. Data collected will include the following:

- Date of deviation
- Type of deviation
- Description of deviation
- Corrective action

The Investigator must maintain accurate, complete, and current records relating to the clinical study. This includes source documents showing the dates and reasons for each deviation from the clinical investigation plan.

8.11 Device Incidents

Any feedback in regards to the Miri- TL should be reported to Esco Global as soon as possible. Feedback may consist of any alleged deficiency related to the physical characteristics, identity, quality, durability, reliability, safety, effectiveness, or performance of the MIRI-TL and/or CultureCoin. Engineering and Quality will investigate device deficiencies and perform an evaluation to determine and document the root cause of any device deficiency. Reports will be filed in the MIRI-TL Study project file and/or in document control. The following data will be collected:

- Date and time incident first observed
- Associated Device(s)
- Description of incident
- Troubleshooting
- Outcome

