3.1 Primary Objective

- To collect safety and imaging data on the MIRI-TL and CultureCoin.

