8.12 Adverse Events

While the overall IVF procedure may involve several visits and procedures, the first time the subject or user has any encounter with the MIRI-TL and CultureCoin is when the embryos are first loaded onto the MIRI-TL for imaging. Adverse

events for the subject or user will be reported from the point of embryos being placed in the MIRI-TL through study completion for each subject. An adverse event will be followed until resolved or stabilized at a level acceptable to the investigator.

Events well documented to be associated with ART/IVF procedures (as outlined in each clinic's consent for IVF procedures) will not be collected as adverse events under this protocol. Other common non-study or non-device related, minor health complaints will not be collected as adverse events (for example: colds, sprains, headaches).

The investigator should follow the reporting requirements of the reviewing IRB/REB for all adverse events (including serious and unanticipated adverse device effects). Documentation of any IRB and Esco Global notifications should be maintained in the site's clinical study files. It is recommended that acknowledgement of receipt from the IRB be maintained in the study file as well.

Adverse events will be reported to Esco Global and data collected will include the following:

- Date of adverse event
- Type of event and description
- Action/treatment taken
- Severity of event
- Seriousness of event
- Investigator's assessment as to the relationship of the AE to the MIRI-TL
- Investigator's assessment as to the relationship of the AE to IVF/ART procedures

Investigator's assessment if the event is a potential Unanticipated Adverse Device Effect (UADE)

Source documentation for adverse events must be collected and filed with the subject's medical chart. Refer to Section 10 – Adverse Event Definitions and Reporting for additional information. Because study procedures are limited to the noninvasive collection of clinical data, no Data Safety Monitoring Board will be established for this study.

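### Device malfunctions are a named safety measure in a study with a comparative safety purpose, but the only procedure that collects them covers the MIRI-TL and CultureCoin and not the control arm's incubators and dishes

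*Combined protocol and SAP*

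**What the plan says.** The Study Purpose row of the synopsis says the study is to show "non-inferior or superior safety and efficacy of the MIRI-TL compared to standard big-box incubators used for embryo culture". The Safety Measures row reads "Adverse events and device malfunctions will be reported and summarized from the start of embryo culture through study exit", with no restriction to either arm.

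The primary objective in section 3.1 is narrower and has no comparator: "To collect safety and imaging data on the MIRI-TL and CultureCoin".

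Section 8.11 puts malfunction reporting into practice. It opens with "Any feedback in regards to the Miri- TL should be reported to Esco Global as soon as possible" and limits the deficiencies in view to the "safety, effectiveness, or performance of the MIRI-TL and/or CultureCoin". The sponsor's engineering and quality functions look for the root cause. The record holds date and time, the device concerned, a description, troubleshooting and outcome.

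Under section 8.1, control patients' oocytes and embryos are cultured in a standard dish in a standard incubator. Section 7 plans 300 patients for the MIRI-TL group and 200 for standard culture.

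**The concern.** A comparison of safety on malfunctions needs a count and an exposure in each arm, gathered under one definition. The plan names the measure and the comparison, then collects the measure for one side only. A gas or temperature excursion in a standard incubator, or a fault in a standard dish, would have no directed place in the study record.

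At stake is one of the two named safety measures. The MIRI-TL incident count could be described, but a reader could not tell whether it was high, low or ordinary for this laboratory. Control incidents that are not recorded at the time may not be recoverable later.

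**Working it through.** The plan states no malfunction rate, safety margin or safety sample size, so there is no figure to reproduce. The check is mainly a reading of the sections against one another.

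**1. Is the measure comparative?** The synopsis purpose is comparative, and its malfunction measure names no arm. The primary objective in 3.1 could be met with MIRI-TL data alone. The conflict is therefore between the synopsis purpose and section 8.11.

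**2. Does any other section capture a control-incubator failure as such?**
- 8.10 (deviations) covers an investigator or site staff not following the plan. Equipment failure is not that.
- 8.12 (adverse events) covers events in the subject or user, "reported from the point of embryos being placed in the MIRI-TL through study completion for each subject". Control embryos never reach that starting point. The device causality item is also specific to one device: "Investigator's assessment as to the relationship of the AE to the MIRI-TL". Correcting the start point would still not record an excursion that harmed no subject or user.
- 8.13 (study exit) would record a cancelled cycle in either arm and has a free-text reason, but it does not ask about equipment.
- 8.1 to 8.3 collect fertilisation counts and embryo assessments in both arms. Damage to embryos would show in these data, but not its cause.

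So no section directs that a standard-incubator or standard-dish incident be recorded.

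**3. What can be estimated as written?** Only a single-arm statement. For example, zero incidents in 300 MIRI-TL patients would give a one-sided 95% upper bound of 1 − 0.05^(1/300) = 0.0099, about 1.0%, treating patients as independent. No difference, ratio or non-inferiority bound is available.

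**4. What would control-arm recording add?** This is an illustration under assumptions that are not in the plan: full recruitment, 5 to 7 culture-days per patient, and the same true incident rate in both arms.
- Exposure, MIRI-TL: 300 × 5 = 1500 to 300 × 7 = 2100 culture-days.
- Exposure, standard culture: 200 × 5 = 1000 to 200 × 7 = 1400 culture-days. The exposure ratio is 1.5 throughout.
- Expected incidents at 3 per 1000 culture-days: 4.5 to 6.3 (MIRI-TL) and 3.0 to 4.2 (standard culture).
- Interval: given a total of n = a + b incidents, a is binomial with p = 1.5R/(1.5R + 1), where R is the rate ratio. Take the exact (Clopper-Pearson) limits for p and convert with R = p / [1.5(1 − p)].

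| Assumed rate per 1000 | Incidents, MIRI-TL v standard | Rate ratio | Exact 95% interval |
|---|---|---|---|
| 1 | 2 v 1 | 1.3 | 0.07 to 79 |
| 3 | 5 v 3 | 1.1 | 0.22 to 7.2 |
| 3 | 6 v 4 | 1.0 | 0.24 to 4.8 |
| 10 | 15 v 10 | 1.0 | 0.42 to 2.5 |
| 10 | 21 v 14 | 1.0 | 0.48 to 2.1 |

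Counts are rounded from rate × exposure. For 5 v 3, the limits for p are 0.245 and 0.915, giving 0.245/(1.5 × 0.755) = 0.22 and 0.915/(1.5 × 0.085) = 7.2.

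Even at the highest assumed rate, a twofold excess is not excluded. These intervals also treat incidents as independent per patient-day. Incubators are shared, and one failure can affect several patients, so the intervals are approximate.

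**The case against.** The strongest reply is that 8.11 is a manufacturer's complaint procedure, naturally limited to the sponsor's own product, and that it serves the primary objective as worded. That is a fair description, and it is a reason to leave 8.11 alone. It does not supply the missing data: 8.11 is also the only source for a measure that the synopsis says will be reported and summarised in a study with a comparative safety purpose.

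A second reply is that the text never excludes the control arm. The synopsis wording is open, the incident record has a general field for the device concerned, and the case report forms are not in the documents. This stands in part. A control entry would be possible, but no procedure asks for one.

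Third, no between-arm malfunction analysis is specified in section 7, and few events would make one weak. This stands, and it limits the point in two ways. First, a reader might infer that the malfunction table will show a zero for control and make the MIRI-TL look worse. The documents plan no such table, and data not collected are properly shown as not collected. Second, the remedy would yield descriptive data, as the intervals above show.

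Finally, the adverse-event rules in 8.12 have the same MIRI-TL anchor, so the two can be corrected in one amendment. Correcting 8.12 alone would still leave equipment failures in the control arm unrecorded.

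**Conclusion.** The point holds as a mismatch between a stated comparative safety purpose and one-arm collection of a named safety measure. As written, malfunctions have no control-arm data for the planned 200 standard-culture patients and cannot contribute to the comparison with standard incubators. The conclusion rests on the named scope of 8.11 and the absence of any standard-incubator provision elsewhere, not on an explicit exclusion.

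A reader might go further and infer that the whole safety and efficacy comparison is lost. The documents do not support that: embryo assessments, pregnancy tests and ultrasound results are collected in both arms. What is missing is the ability to identify and count equipment failures on the control side.

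The practical size cannot be stated from the plan, because it gives no incident rate. Under the assumed rates of 1 to 10 per 1000 culture-days, two-arm recording would give a rough description and would not by itself establish non-inferiority. The change should be made because it is cheap and bears directly on the study's stated question.

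**What to change.** Leave sponsor complaint reporting for the MIRI-TL and CultureCoin in 8.11 as it is. Add a study incident record for the incubators and dishes in both arms, with:
- one definition of an incident for both device types;
- the same window, from placement of inseminated oocytes in culture until the last embryo leaves culture;
- the incubator or chamber involved, and the number of patients and of oocytes or embryos affected.

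In section 7, state that incidents and embryos affected will be summarised by arm, descriptively and with exposure. State also that any interval is approximate because one failure can affect several patients, and that the data will not by themselves establish non-inferiority.

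If control-arm recording is not adopted, say in the synopsis and in section 7 that malfunction data describe the MIRI-TL only and form no part of the comparative safety claim.

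The cost is one additional record at a single site and some data entry. Detection may still differ between device types, and this should be noted when the counts are interpreted.
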